3.5 Methods for assigning treatment groups

The research center number must be marked before subject ID with two digitals. Subject ID will be consecutively numbered by the enrollment order. If a subject withdraws from the study during the study, the subject ID can no longer be used, and the withdrawn subject can no longer participate in the study.

3.6 study restriction

During the course of this study, any lipid-lowering medication other than the study drugs , antidiabetic agents, herbal medication, and weight-losing drugs are prohibited. All other drugs should be maintained as a stable dosage if possible.

3.7. Discontinuation of Study Drug

3.7.1. Permanent Discontinuation of Study Drug

For all participants who permanently discontinue study medication, the participants will still be part of the study, and outcome events and vital status must be reported until the common study end date. Discontinuing an investigational drug is usually the only available therapy to treat suspected Drug-Induced Liver Injury (DILI) , drug-induced kidney injury(DKI),and may not result in an immediate improvement as test values and symptoms can last (sometimes even progress) for days or weeks after the drug has been discontinued. Once discontinued, patients should not be re-exposed

to the suspected drug.

The study drugs should be discontinued in case

1) Meeting the criteria of possible Drug-Induced Liver Injury(FDA guidance)

- ALT or AST >8 ULN
- ALT or AST >5 ULN for more than 2 weeks
- ALT or AST >3 ULN and (TBL >2 ULN or INR >1.5)
- ALT or AST >3 ULN with the appearance of fatigue, nausea, vomiting, right upper quadrant pain or tenderness, fever, rash, and/or eosinophilia (>5%)

2) Diagnosis of rhabdomyolysis

● The clinical manifestations of rhabdomyolysis include myalgias, weakness, red to brown urine due to myoglobinuria, and elevated serum muscle enzymes. An acute elevation in the CK and other muscle enzymes and a decline in these values within three to five days of cessation of muscle injury. The CK is typically at least five times the upper limit of normal and is frequently greater than 5000 international units/L. The degree of myalgias and other symptoms varies widely, and some patients are asymptomatic. Fever, malaise, tachycardia, and gastrointestinal symptoms may be present.

● Other manifestations include fluid and electrolyte abnormalities, many of which precede or occur in the absence of acute kidney injury, and hepatic injury. Hypovolemia, hyperkalemia, hyperphosphatemia, hypocalcemia, hyperuricemia, and metabolic acidoses may be seen. Hyperkalemia may result in cardiac dysrhythmias. Later complications include acute kidney injury (AKI), hypercalcemia, compartment syndrome, and, rarely, disseminated intravascular coagulation.

3) Pregnancy;

4) The investigator considers that study drug is harmful to the safety or health of the participants;

5) Participants request to stop using the test drug;

6) Sponsor requires participants to permanently stop taking study drug

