1.3 Benefit/risk and ethical assessment

Benefit:

Evidence showed that XZK treatment by reducing LDL-C levels and TG levels significantly reduces the risk of CHD events by 45%. Therefore, for the clinical benefit of dyslipidemia patients with prediabetes , they will get expert advice and guidance of lipid management from physicians.

Potential risk:

Risk associated with Study Drug:

XZK capsule is a modernized proprietary Chinese medicine product with modern pharmaceutical technology and strict Good management practices (GMP)production management. A few mild or moderate gastrointestinal (GI) effects may occur when taking XZK, but a large number of clinical application results show that XZK capsule is safe and with few side effects [1].

Atorvastatin decrease cholesterol production in the liver by preventing the conversion of HMG-CoA to mevalonate. Common side effects to Atorvastatin include gastrointestinal (GI) effects, headache, and mild muscle pain. Rare side effect include rhabdomyolysis, dark urine, jaundice, etc.

Participants with high potential risk (meet one of the Exclusion Criteria) will not be eligible for enrollment . Moreover, we will minimize this risk by mandating adequate follow-up visit to ensure clinical assessment(e.g.CK and liver enzymes (ALT, AST)) during study participation . Local Investigator and the sponsor will also collect and report serious adverse events according to regulations. The study drug will be discontinued immediately, if any ADR occurs during the study.

Risk associated with Study Procedure:

In view of the few patients with prediabetes receive drug treatment and Statins are the most effective and acceptable drugs to treat dyslipidemia, patients may be initially hesitant to participant in this study. Previous studies have reported that XZK is effective in blood lipid reduction. We will provide the patients with pre-study education on dyslipidemia medication therapy.

Loss to follow up is another risk factor which can affect the incident rate in statistical analysis and outcome. However, this study is designed for 24 weeks short intervention and contains 5 visits with the assistance of local investigators and experienced CRO team. Therefore, we are confident to limit the loss to follow up rate.

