4 STUDY PLAN AND TIMING OF PROCEDURES

4.1 Study Plan

Table 1 Study plan

		Screening	Rando misatio n	Treatment Phase		
Visits		Visit 0	Visit 1	Visit 2	Visit 3	Visit 4
Timelines(week)		-1	0	4	12	24
Treatment Days		7 +3	0	29 ±7	85 ±7	169 ±7
Informed Consent signed		×				
Eligibility criteria		×	×			
General information	Demographics		×			
	Medical History		×			
	Physical examination		×	×	×	×

Medications	Concomitant medications		×	×	×	×
Clinical assessment	Serum lipids (TG/non HDL-C/TC/LDL-C)		×	×	×	×
	HbA1c		×		×	×
	Plasma Glucose (PG), insulin, C-peptide levels at fasting and 2 h after drinking glucose solution(75g glucose)		×	×	×	×
	Hepatic function (Bilirubin, albumin, liver enzymes)		×	×		×
	Creatine kinase (CK)		×	×		×
	Renal function (Serum creatinine, BUN ,eGFR)		×	×		×
	Routine blood test		×			×
	Pregnancy test (HCG test for women of childbearing potential only)		×			
	ECG		×			×
	Adverse events		×	×	×	×
Questionnaire	IPAQ		×	×	×	×
Other work	Distributing study drugs		×	×	×	
	Patient medication guidance		×	×	×	
	Patient lifestyle guidance	×	×	×	×	×
	Patient diary dispensance	×	×	×	×	×
	Drug accountability log cards		×	×	×	×
	Retrieving drugs			×	×	×

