4.2.2 Randomization and treatment period (Visit1-Visit4)

Subjects won't be able to eat or drink anything for eight hours before visit 1, visit 2, visit 3 and visit 4.

Visit 1 (Randomization)

1. Before randomization, the investigator should complete the following actions and collect the relevant data:

- Collect general information:

Demographics data: gender, date of birth, education, insurance
- Retrieving and reviewing the Patient Diary
- Collect the information of clinical assessment such as Serum lipids (TG/non HDL-C/TC/LDL-C), HbA1c , Plasma Glucose (PG), PPG, insulin and C-peptide at fasting and 2h after glucose solution (75g glucose) . Hepatic function (Bilirubin, albumin, liver enzymes), Creatine kinase (CK), Renal function (Serum creatinine, BUN ,eGFR), Routine blood test, Pregnancy test (HCG test for women of childbearing potential only),and ECG. According to the results of the above tests, screen the patients again.
- Eligibility criteria: To verify the participants satisfy all the inclusion criteria and without any exclusion criteria.

2. Randomization.

3. Medical history: Including previous medical history, treatment before screening and other comorbidities.

4. Physical examination: blood pressure, pulse rate, weight, height.

5. Collect the information of Concomitant medications.

6. Collect the information of history of adverse events with statins.

7. Collect physical activity information: Physical activity level by for Measurement of a Person's Habitual Physical Activity (IPAQ)

8. Patients should be guided for medication.

9. Distribute study drugs by groups, patients should start the treatment after the day of randomization

Visit 2 (4 weeks after treatment phase)

1. Collect the information of Concomitant medications.
2. Collect the information of adverse events. If any AE is reported, relevant laboratory test should be collected.
3. Collect the information of clinical assessment such as Serum lipids (TG/non HDL-C/TC/LDL-C), Plasma Glucose (PG), PPG, insulin and C-peptide at fasting and 2h after drinking glucose solution (75g glucose) . Hepatic function (Bilirubin, albumin, liver enzymes), Creatine kinase (CK), Renal function (Serum creatinine, BUN ,eGFR).
4. Collect physical activity information: Physical activity level by for Measurement of a Person's Habitual Physical Activity (IPAQ)
5. Patients should be guided for medication and lifestyle
6. Review of the patient's diary, compliance to study medication

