7. Distribute study drugs by groups.
8. Retrieving drugs and log cards

Visit 3 (12 weeks after randomization)

1. Collect the information of Concomitant medications.
2. Collect the information of adverse events. If any AE is reported, relevant laboratory test should be collected.
3. Collect the information of clinical assessment such as Serum lipids (TG/non HDL-C/TC/LDL-C), HbA1c, Plasma Glucose (PG), insulin and C-peptide at fasting and 2 h after drinking glucose solution (75g glucose) .
4. Collect physical activity information: Physical activity level by for Measurement of a Person's Habitual Physical Activity (IPAQ)
5. Patients should be guided for medication and lifestyle
6. Review of the patient's diary, compliance to study medication
7. Distribute study drugs by groups.
8. Retrieving drugs and log cards

Visit 4 (24 weeks after randomization)

1. Collect the information of Concomitant medications.
2. Collect the information of adverse events. If any AE is reported, relevant laboratory test should be collected.
3. Collect the information of clinical assessment such as Serum lipids (TG/non HDL-C/TC/LDL-C), HbA1c , Plasma Glucose (PG), PPG, insulin and C-peptide at fasting and 2h after glucose solution (75g glucose) ,Hepatic

function (Bilirubin, albumin, liver enzymes), Creatine kinase (CK), Renal function(Serum creatinine, BUN ,eGFR), Routine blood test, and ECG.

4. Collect physical activity information: Physical activity level by for Measurement of a Person's Habitual Physical Activity (IPAQ)
5. Patients should be guided for medication and lifestyle
6. Review of the patient's diary, compliance to study medication
7. Retrieving drugs and log cards

4.3 lifestyle modification

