6.2 Serious adverse event

An AE is considered a serious AE (SAE) if it fulfills one or more of the following criteria:

- Results in death
- Is life-threatening
- Requires or prolongs hospitalization
- Is a congenital anomaly or birth defect
- Is a persistent or significant disability/incapacity
- Is another important medical event in the opinion of the investigator

The requirement or extension of hospitalization is not considered a SAE if it fulfills one or more of the criteria(see Appendix 2):

SAEs or non-serious AEs that are not study outcomes and are not expected as part of normal treatment and progression of the disease or expected with the treatment with Xuezhikang and atorvastatin, must be reported. All SAEs, all non-serious AEs leading to permanent discontinuation of study-drug treatment and non-serious AEs which the investigator considers of particular concern will be recorded on the Adverse Event Report form.

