6.9 Adverse events based on examinations and tests

Deterioration as compared to baseline in protocol-mandated including laboratory values, vital signs should therefore only be reported as AEs if they fulfil any of the SAE criteria or are the reason for discontinuation of treatment with the investigational product.

If deterioration in a laboratory value/vital sign is associated with clinical signs and symptoms, the sign or symptom will be reported as an AE and the associated laboratory result/vital sign will be considered as additional information. Wherever possible the reporting Investigator uses the clinical, rather than the laboratory term (e.g., anaemia versus low haemoglobin value). In the absence of clinical signs or symptoms, clinically relevant deteriorations in non-mandated parameters should be reported as AE(s). Deterioration of a laboratory value, which is unequivocally due to disease progression, should not be reported as an AE/SAE. Any new or aggravated clinically relevant abnormal medical finding at a physical examination as compared with the baseline assessment will be reported as an AE.

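### The stopping criterion for ALT/AST above 5 ULN lasting over 2 weeks needs a second liver value that the protocol does not require until Visit 4, 140 days after Visit 2

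*Protocol*

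**What the plan says.** Protocol section 3.7.1 lists four liver criteria for permanent discontinuation:

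- ALT or AST above 8 ULN;
- "ALT or AST >5 ULN for more than 2 weeks";
- above 3 ULN together with raised bilirubin (TBL) or INR;
- above 3 ULN with symptoms or eosinophilia.

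Section 6.3 uses the same four to define an event needing additional data collection.

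In Table 1 (section 4.1) the row beginning "Hepatic function (Bilirubin, albumin, liver enzymes" is marked at Visits 1, 2 and 4 and is blank at Visit 3. The visit lists in section 4.2.2 agree. Visit 3 calls for serum lipids and "HbA1c, Plasma Glucose (PG), insulin and C-peptide at fasting and 2 h after drinking glucose solution (75g glucose", with no liver test.

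The only extra testing is conditional on an adverse event: "If any AE is reported, relevant laboratory test should be collected". Section 6.9 says that deteriorations in mandated laboratory values "should therefore only be reported as AEs if they fulfil any of the SAE criteria or are the reason for discontinuation of treatment". One of the SAE criteria in 6.2 is a judgement: "Is another important medical event in the opinion of the investigator".

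Section 1.3 adds two general statements. One is "The study drug will be discontinued immediately, if any ADR occurs during the study". The other is that "we will minimize this risk by mandating adequate follow-up visit to ensure clinical assessment(e.g.CK and liver enzymes (ALT, AST)) during study participation".

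**The concern.** A criterion based on duration cannot be judged from one sample. The protocol fixes a numerical threshold and a duration, but it neither requires nor times the second measurement that would show the duration.

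If the schedule is followed exactly as written, a patient with a week-4 ALT of, say, 6 ULN, normal bilirubin and no symptoms is given drug again at Visits 2 and 3. No further liver result is required before Visit 4. Whether a persistent rise is confirmed and acted on is then left to each investigator at about 20 sites. The matching event in 6.3 may be ascertained unevenly for the same reason.

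Section 3.7.1 itself says that stopping the drug is usually the only treatment for suspected drug-induced liver injury, and that injury can progress after the drug is stopped. A delay in applying the criterion therefore matters to the patient concerned.

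A related, secondary gap is that a symptom-free rise beginning after Visit 2 appears on no scheduled liver result until Visit 4.

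**Working it through.** **Inputs.** From Table 1: Visit 2 on day 29 ±7 (22 to 36), Visit 3 on day 85 ±7 (78 to 92), Visit 4 on day 169 ±7 (162 to 176). Treatment lasts 24 × 7 = 168 days. Exclusion criterion 7 removes patients with baseline ALT or AST above 3 ULN. The criterion needs more than 14 days.

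**Which required values can show persistence.** Visit 1 cannot be the first raised value, because above 3 ULN at baseline is excluded. The first required value that can exceed 5 ULN is at Visit 2. The next required value is at Visit 4.

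**Gap between them.**
- Nominal: 169 − 29 = 140 days, the same as (24 − 4) × 7.
- Shortest: 162 − 36 = 126 days. Longest: 176 − 22 = 154 days.
- Against the 14-day criterion: 140 / 14 = 10 times (126 / 14 = 9 to 154 / 14 = 11).

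By Visit 4 the criterion can no longer work as a stopping rule. At the earliest, day 162, at most 168 − 162 = 6 treatment days remain, and drug is collected at that visit with none dispensed. Two raised values 140 days apart would not by themselves show a sustained rise either.

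**Do the other criteria cover this patient?**
- Above 8 ULN: applicable from the week-4 panel, but not met at 5 to 8 ULN.
- Above 3 ULN with TBL or INR: the TBL part is applicable from the week-4 panel, but not met here. INR is not in Table 1.
- Above 3 ULN with symptoms or eosinophilia: symptoms are picked up through adverse-event collection, but this patient has none. The routine blood test is scheduled only at Visits 1 and 4.

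**Does other text supply the second value?**
- AE-triggered tests (4.2.2): under 6.9 this rise is an adverse event only if the investigator judges it an important medical event or stops drug because of it. Even then no test date is set.
- ADR stop (1.3): depends on suspected causality (6.1.2).
- Section 3.7.1 item 4: investigator judgement.
- Section 3.7.2 item 1: refers back to the 3.7.1 thresholds, so it has the same gap.
- Section 3.7.3: governs restarting after a stop, not whether a rise has persisted.

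**With a repeat 15 to 21 days after the Visit 2 sample.**
- Nominal day: 29 + 15 = 44 to 29 + 21 = 50, which is 169 − 44 = 125 to 169 − 50 = 119 days before Visit 4.
- Extremes with windows: day 22 + 15 = 37 to day 36 + 21 = 57. The latest is still 78 − 57 = 21 days before the earliest Visit 3, so the result can be known before drug is dispensed there.

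**With a liver panel at Visit 3.**
- Visit 2 to Visit 3: 85 − 29 = 56 days (78 − 36 = 42 to 92 − 22 = 70).
- Visit 3 to Visit 4: 169 − 85 = 84 days (162 − 92 = 70 to 176 − 78 = 98).
- The longest scheduled on-treatment gap falls from 140 to 84 days. Since 56 days still far exceeds 14, this panel does not replace the repeat.

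**The case against.** The strongest reply is that the duty to retest is implicit. An investigator who sees a value above 5 ULN cannot honour the criterion without measuring again, nothing forbids an unscheduled test, and 6.9 limits what is reported as an adverse event, not clinical follow-up. Because baseline values above 3 ULN are excluded, a week-4 value above 5 ULN is a new rise on treatment. If causality is suspected, section 1.3 stops the drug at once and the two-week criterion is never needed.

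Much of this stands. It makes the exposed group small, and a sensible investigator would often retest or stop. What it does not do is require or time the second value. Section 3.7.1 attributes its criteria to regulatory guidance that is not at hand. Whatever that source says about retesting, the protocol carries no such step.

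A reader might infer that section 1.3 promises a liver test at every follow-up visit and that Table 1 breaks the promise. The wording does not go that far, and tests at weeks 4 and 24 can satisfy it. A reader might also set the immediate ADR stop in 1.3 against 3.7.2, which confines withdrawal to clinically important related events or a contraindication. For a related rise judged clinically important, both allow stopping, so they do not collide for this patient.

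It is also fair to say that the ratio of 9 to 11 compares intervals and does not measure harm.

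**Conclusion.** The point holds in a narrow form. For a symptom-free patient with ALT or AST above 5 and up to 8 ULN and TBL not above 2 ULN at Visit 2, this criterion cannot be applied from required tests until Visit 4. That is 140 days later (126 to 154), as treatment ends. It is a stated safety rule that the protocol's own schedule cannot operate, and test schedules and stopping rules belong in the protocol, not in a statistical analysis plan.

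The conclusion assumes that a rise lasting more than 2 weeks has to be shown by two values more than 14 days apart. The empty Visit 3 cell is confirmed by the Visit 3 list, so it is not a fault of the table.

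Three stronger readings are not supported. The liver rules as a whole are not unworkable, since the 8 ULN, TBL and symptom criteria can be applied. It does not follow that such a patient would be left on drug, because investigators may stop or retest. No effect on the HbA1c endpoint follows. The documents give no rate for this subgroup, so no patient count is claimed.

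**What to change.** **Main change**, in sections 3.7.1 and 6.3, add:

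> Any ALT or AST >5 ULN is repeated, with TBL, 15 to 21 days after the first raised sample unless study drug has already been stopped. If still >5 ULN, study drug is permanently discontinued.

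The existing thresholds and investigator judgement stay as they are. Saying *permanently* matters because 3.7.2 also sends the 3.7.1 thresholds to temporary stopping with a restart at a lower dose, whereas 3.7.1 bars re-exposure.

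**Second change:** add hepatic function to the existing Visit 3 blood draw in Table 1 and 4.2.2, with the result checked against 3.7.1. Rises that begin after week 4 can then be seen before treatment ends. A repeat after a raised Visit 3 value would fall on about day 100 to 106 (85 + 15 to 85 + 21), 63 to 69 days before Visit 4.

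**Cost:** a short amendment, unscheduled visits only for patients above 5 ULN (number not given, expected to be few), and at most 392 inexpensive panels, or about 392 × 0.9 = 353 at the planned 10% dropout. The downside is those extra visits and more results to review.

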3.7.2. Temporary Discontinuation of Study Drug

Adherence to the study drug will be evaluated and reinforced at every study visit. Participants who temporarily discontinued study drug should be re-challenged when applicable. Study drug should only be withdrawn if a clinically important adverse event related to the study medication occurs or the participant develops a contraindication.

The following conditions may lead to Temporary Discontinuation of Study Drug:

- 1) Predefined security thresholds are met (abnormal laboratory test findings , see detail in Section 3.7.1)
- 2) In case of AE/SAE or other causes, the investigator should consider temporarily discontinuing the drug

If the safety threshold is reached and the drug is temporarily discontinued, treatment will resume after approximately 2-4 weeks and be restarted at a lower dose

If the study drug is discontinued due to AE/SAE and there are no safety concerns any more (i.e., no causality in medical judgment; other transient symptoms) the investigator should try his/her best efforts to resume the clinical drug trail .

Other causes are defined as events that lead to study drug discontinuation and are not considered an AE/SAE, such as elective hospitalization without emergencies.

All temporary discontinuations should be recorded in the eCRF.

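### Section 3.7.2 allows a restart after the same liver-injury limits that Section 3.7.1 treats as grounds for a permanent stop without re-exposure

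*Protocol*

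**What the plan says.** Section 3.7.1 of the protocol (Permanent Discontinuation) says of suspected drug-induced liver or kidney injury: "Once discontinued, patients should not be re-exposed" to the suspected drug. Its first reason to stop is possible DILI, defined by four criteria:

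- ALT or AST above 8×ULN;
- ALT or AST above 5×ULN lasting over two weeks;
- "ALT or AST >3 ULN and (TBL >2 ULN or INR >1.5";
- "ALT or AST >3 ULN with the appearance of fatigue, nausea, vomiting", or other listed symptoms or eosinophilia.

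Item 4 adds a judgment-based reason: "The investigator considers that study drug is harmful to the safety or health of the participants".

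Section 3.7.2 opens its list with "The following conditions may lead to Temporary Discontinuation of Study Drug". The first condition is "Predefined security thresholds are met (abnormal laboratory test findings , see detail in Section 3.7.1". When such a threshold has led to a temporary stop, "treatment will resume after approximately 2-4 weeks and be restarted at a lower dose". A separate sentence deals with stops for adverse events and is conditional: "If the study drug is discontinued due to AE/SAE and there are no safety concerns any more".

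Section 3.7.3 says that rechallenge should generally not be attempted when transaminases exceed 5×ULN. It gives no limit at or below that level.

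**The concern.** The two sections use one set of laboratory limits for two incompatible actions. A site that applies 3.7.1 stops the drug for good. A site that applies 3.7.2 may pause it and then restart within about a month, without having to show that the liver tests have recovered.

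Take a patient with ALT at 4×ULN and bilirubin above 2×ULN. This patient meets a DILI criterion in 3.7.1, lies below the level at which 3.7.3 advises against rechallenge, and can be restarted under 3.7.2. At stake is re-exposure of someone with possible drug-induced liver injury to the suspected drug. No claim is made about bias in the HbA1c comparison.

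**Working it through.** **1. Which limits does 3.7.2 refer to?** Section 3.7.1 contains no second, milder set of laboratory thresholds. Its CK figure only describes how rhabdomyolysis usually presents. The DILI limits are therefore the only ones set there as criteria. Section 6.3 lists the same four as DILI.

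**2. Each criterion against the three rules.**

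| DILI criterion in 3.7.1 | 3.7.1 | 3.7.2 | 3.7.3 (general advice above 5×ULN) |
|---|---|---|---|
| >8×ULN | permanent stop | pause, then restart | covers it |
| >5×ULN for over 2 weeks | permanent stop | pause, then restart | covers it |
| >3×ULN plus bilirubin >2×ULN or INR >1.5 | permanent stop | pause, then restart | silent from >3 to 5×ULN |
| >3×ULN plus symptoms or eosinophilia | permanent stop | pause, then restart | silent from >3 to 5×ULN |

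For the first two rows, 3.7.3 supports the permanent stop but conflicts with the restart sentence of 3.7.2. For the last two, nothing decides between 3.7.1 and 3.7.2 in the range above 3 and up to 5×ULN. Exclusion criterion 7 (Section 3.2) keeps out patients with baseline ALT or AST above 3×ULN, so any of these limits reached on treatment is a new crossing.

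**3. How soon would a liver test follow a restart?** Inputs from Table 1 (Section 4.1): Visit 2 on day 29, Visit 3 on day 85, Visit 4 on day 169, each ±7 days. On treatment, hepatic function is scheduled at Visits 2 and 4 but not at Visit 3. Assume the stop occurs at Visit 2.

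- Restart day: 29 + 14 = 43 to 29 + 28 = 57.
- Scheduled tests only (Visit 4): 169 − 57 = 112 to 169 − 43 = 126 days, that is 16 to 18 weeks. With windows: (169 − 7) − (29 + 7 + 28) = 98 to (169 + 7) − (29 − 7 + 14) = 140 days.
- If an adverse event prompts a test at Visit 3, as Section 4.2.2 provides: 85 − 57 = 28 to 85 − 43 = 42 days, that is 4 to 6 weeks. With windows: (85 − 7) − (29 + 7 + 28) = 14 to (85 + 7) − (29 − 7 + 14) = 56 days.

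**4. The lower dose.** Neither arm has one defined. Section 7.2 and the protocol summary give atorvastatin only as one 20 mg tablet a day.

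**The case against.** The strongest reply is that a site can satisfy both sections by stopping permanently. Section 3.7.1 is the specific rule, whereas 3.7.2 only says that its conditions may lead to a temporary stop, and its restart sentence applies only once that route has been taken. This is right as far as it goes: nothing forces a site to choose the temporary route. But 3.7.2 offers that route for exactly these limits, and for a patient who takes it the restart is written as what will happen.

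Other provisions also help:

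- **Adverse-event route.** Section 6.3 names the four criteria among the adverse events needing extra data, and under Section 6.9 an abnormal value that causes discontinuation can be reported as one. The restart condition for adverse events in 3.7.2 could then apply, and suspected drug-induced injury would fail it. However, that condition stands in its own sentence, and neither 6.3 nor 6.9 carries it over to the threshold sentence.
- **Immediate stop.** Section 1.3 requires the drug to be stopped at once for any adverse drug reaction. It does not say whether the stop is permanent.
- **Investigator judgment.** Item 4 of 3.7.1 permits a permanent stop. The objective criteria in item 1 are there so that the decision does not rest on judgment alone.
- **Unscheduled testing.** The two-week criterion needs a repeat test, and INR is not in Table 1, so extra tests are presupposed. The 16 to 18 weeks is thus the gap on scheduled tests alone, and unscheduled tests could shorten it.

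These points narrow the opening. None closes it.

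**Conclusion.** The concern holds. Sections 3.7.1 and 3.7.2 give contradictory instructions for all four possible-DILI criteria. Section 3.7.3 largely settles two of them in favor of a permanent stop. It leaves the two criteria that start at 3×ULN unresolved for values above 3 and up to 5×ULN. The conclusion rests on reading the cross-reference in 3.7.2 as pointing to the DILI limits, the only candidates in 3.7.1.

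The intervals after restart assume a stop at Visit 2 and no other unscheduled test. The number of patients affected cannot be derived from the protocol. Because this is a hepatic stopping rule and the possible harm is serious, it must be corrected even if few patients would meet it. The undefined lower dose is a genuine but secondary gap.

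**What to change.** 1. In 3.7.1 and 3.7.3, state that meeting any possible-DILI criterion means permanent discontinuation without rechallenge, whatever the transaminase level.
2. In 3.7.2, delete the reference to 3.7.1. Limit threshold-driven interruption to separate, milder laboratory limits set by the medical team. Require a repeat liver test showing recovery before restart and an early liver test after it.
3. Secondary: remove the lower-dose restart or define the dose for each arm.

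The cost is a wording amendment and a letter to sites. There may be a few more permanent discontinuations, but under 3.7.1 those patients stay in follow-up. A few extra liver tests would be needed for patients who restart after a milder threshold.
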